### Statistical Methods

This is a randomized Phase 2, multicenter, open-label study with 2 separate, parallel disease cohorts (MDS and AML).

The study will be conducted in 2 stages for each disease cohort (Section 9.3). Subjects will be randomized with 1:1 ratio to receive subcutaneous azacitidine monotherapy or subcutaneous azacitidine in combination with durvalumab.

The randomization procedure will be accomplished by a validated Interactive Response Technology (IRT). At randomization, subjects will be stratified by cytogenetic risk, very good, good and intermediate versus poor or very poor for MDS cohort, and intermediate versus poor for AML cohort.

In the MDS cohort, the primary efficacy endpoint is the overall response rate (defined as CR, mCR, PR, and/or HI) as determined using the IWG 2006 response criteria for MDS. The null hypothesis of the response rate ( $H_0 : p \leq 36\%$ ) will be tested against the alternative hypothesis of the response rate ( $H_1 : p \geq 72\%$ ) with a type I error rate of 5% and 90% power. A total of 72 subjects will be randomized. An interim analysis for futility purpose will be conducted when 30 subjects have completed 6 cycles of treatment (See Section 9.3.1).

In the AML cohort, the primary efficacy endpoint is overall response rate (CR or CRi) based on modified IWG 2003 response criteria for AML. The null hypothesis of the response rate ( $H_0 : p \leq 25\%$ ) will be tested against the alternative hypothesis of the response rate ( $H_1 : p \geq 50\%$ ) with a type I error rate of 5% and 80% power. A total of 110 subjects will be randomized. An interim analysis for futility purposes will be conducted when 50 subjects have completed 6 cycles of treatment (see Section 9.3.2).

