## 9.6.1. Primary Efficacy Analysis

### 9.6.1.1. Primary Efficacy Endpoint

The primary efficacy endpoint will be programmatically derived using the results/assessments generated by the central morphologic/cytogenetic and hematology laboratories. This analysis will be conducted after completion of the Stage 1 and Stage 2 portions of the study. A subject is considered evaluable for response if they have undergone the disease status assessment following treatment Cycle 6. Subjects who discontinue from the treatment phase before the first postbaseline efficacy assessment (following treatment Cycle 3) and will be replaced unless the subject had a documented progression of their disease or died will be considered as nonresponders. If one postbaseline disease assessment is performed, this assessment would be considered for response.

The primary efficacy analysis will be based on the ITT population. Analysis based on the EE population will be confirmative and supportive. Test statistics on the difference of proportion of overall response between monotherapy arm and combination therapy arm using unpooled estimate of variance will be used for the primary efficacy endpoint analysis along with confidence intervals.

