4.2. Stratification, Randomization, and Blinding

The study will be conducted in 2 stages for each disease cohort (Section 9.3 of the protocol). Subjects will be randomized with 1:1 ratio to receive subcutaneous azacitidine alone or subcutaneous azacitidine in combination with durvalumab.

The randomization procedure will be accomplished by a validated Interactive Response Technology (IRT). At randomization, subjects will be stratified by cytogenetic risk: very good, good, intermediate versus poor or very poor for the MDS cohort ([Appendix 17.4](#), IPSS-R Cytogenetic Risk Groups), and intermediate versus poor for the AML cohort ([Appendix 17.5](#)).

This study will employ dynamic randomization based on two stratification factors (defined above) to achieve an even treatment balance between (A) Combination and (B) Monotherapy.

Step 1: Determine Primary (Disease Type) and Secondary (Cytogenetic Risk Factor) Stratification Factors

Subjects will first be stratified based on the disease type of either MDS or AML, as the secondary stratification factor variable depends on this information. Once disease type has been identified, the secondary stratification factor of cytogenetic risk factor can be identified. Cytogenetic risk factor options for each disease type are as follows:

- MDS: Very good, good and intermediate vs. Poor and Very Poor
- AML: Intermediate vs. Poor

Step 2: Determine Evaluable Subjects

Only evaluable subjects will be considered when dynamic randomization is performed. Evaluable subjects are those who have been randomized and NOT been marked as replacement eligible via the Replacement Eligibility Review admin module.

Step 3: Determine Set of Ranges

To achieve treatment balance the measure of variability needs to be defined and is a quantitative way to describe the imbalance of patients amongst the treatment arms. Specifically, the measure of variability for this procedure is the Range which is the difference between the number of patients in the treatment arm with the most patients and the number of patients in the treatment arm with the least patients. For example, if treatment A has 4 patients and treatment B has 3 patients, the Range is 1, ie, 4 (maximum) – 3 (minimum). When a new subject is to be randomized, the potential Ranges will be calculated for each possible treatment assignment. This will provide a Set of Ranges that measures the potential imbalance resulting from assigning a patient to the different treatments.

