For example, the current enrollment (of evaluable subjects) for the MDS disease type is:

	Treatment A	Treatment B
Total Randomized	6	5
Level/Stratum Balance		
Intermediate	4	3
Poor and Very Poor	2	2

The next subject to be randomized has disease type MDS and is Intermediate cytogenetic risk. First step is to calculate the Set of Ranges for the Intermediate level.

If the subject were to be assigned to treatment A the totals would become 5 and 3 and the intermediate level range would be 2, as calculated by Treatment A – Treatment B = 2.

	Treatment A	Treatment B
Intermediate	5	3

If the subject were to be assigned Treatment B the Range would be $4 - 4 = 0$ for the strata.

	Treatment A	Treatment B
Intermediate	4	4

Step 4: Determine the Rank

Continuing with the above example, since Treatment B has the lowest Range, it receives Rank 1 and Rank 2 would be assigned to Treatment A.

Step 5: Determine the Appropriate Cumulative Representation

Using the tables below and considering that in the scenario above, Rank 1 \diamond Rank 2 we would reference Rank Scenario 4 to determine the appropriate Cumulative probabilities. Ultimately based on this Rank Scenario the probability to randomize the patient to treatment A or B will be 1/1 if there is no difference in Rank (Rank Scenario 1 below). Otherwise, the probability will be 9/1 – with the treatment defined as Rank 1 above receiving the higher probability (Rand Scenario 2 below).

Rank Scenario 1: Rank 1 = Rank 2

Rank	Probability	Decimal Probability	Cumulative Probability
Rank 1	1/2	0.5	0.5
Rank 2	1/2	0.5	1.0

Rank Scenario 2: Rank 1 \diamond Rank 2

Rank	Probability	Decimal Probability	Cumulative Probability
Rank 1	9/10	0.9	0.9
Rank 2	1/10	0.1	1.0

Step 6: Query the Random Number table

A table is required that contains a sequence of random numbers between 0.0000 and 1.0000. This list should be uniformly distributed. Based on the next unassigned random number on the list. If the number is \leq Rank 1 cumulative probability, then the treatment in Rank 1 gets the assignment. If the number is $>$ Rank 1 cumulative probability then the treatment in Rank 2 gets the assignment.

Blinding : not applicable for this study.

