4.3. Sample Size

A total of approximately 182 eligible subjects will be enrolled in the study, with a total of 72 subjects in the MDS cohort and 110 subjects in the AML cohort.

A subject who discontinues from the treatment phase before the first postbaseline efficacy assessment (following treatment Cycle 3) will be replaced unless the subject had a documented progression of their disease or died from their disease or died from an IP-related event. An additional subject will be included in that cohort (MDS or AML cohort).

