5.2. Analysis Populations

5.2.1. Intent to Treat Population

The intent to treat (ITT) Population will include all randomized subjects. The primary efficacy analyses will be performed on the ITT Population.

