10.1. Primary Efficacy Endpoint

The primary efficacy endpoint is the ORR and will be programmatically derived using the results/assessments generated by the central morphologic/cytogenetic and hematology laboratories. In case no central hematology results are available within +/- 8 days of bone marrow samples, local hematology results might be used if available. This analysis will be conducted after completion of the Stage 1 and Stage 2 portions of the study. A subject is considered evaluable for response if they have undergone at least one disease status assessment following treatment Cycle 6. Subjects who discontinue from the treatment phase before the first post baseline efficacy assessment (following treatment Cycle 3) will be replaced unless the subject had a documented progression of their disease or died and will be considered as non-responders. If one post baseline disease assessment is performed, this assessment would be considered for response.

The difference of the proportions for overall response between the azacitidine alone and combination therapy arms will be tested using a standard Wald asymptotic two-sided test with unpooled estimate of variance and presented along with corresponding two-sided 95% CIs.

The hypothesis tested will be:

$$H_0: d = 0$$

versus

$$H_a: d \neq 0,$$

Where $d = p_1 - p_2$ is difference in overall response rate in the combination therapy arm (p_1) versus the overall response rate in the monotherapy arm (p_2).

The test statistic is

$$z = \hat{d}/se(\hat{d})$$

Where, the standard error is computed from the sample proportions as

$$se(\hat{d}) = \sqrt{\frac{\hat{p}_1(1 - \hat{p}_1)}{n_1} + \frac{\hat{p}_2(1 - \hat{p}_2)}{n_2}}$$

Where \hat{p}_1 (respectively \hat{p}_2) is the estimated response rate in the combination therapy arm (respectively monotherapy arm) and is derived as the observed response rates in respective arms.

Myelodysplastic Syndromes Cohort

For the MDS cohort, the primary efficacy endpoint is the proportion of subjects achieving an overall response rate (defined as CR, PR, mCR, and/or HI) as determined using the International Working Group (IWG) 2006 response criteria for MDS ([Appendix 17.2](#)). The ORR will be summarized together with two-sided 95% CI. Subjects discontinued before 6-cycle treatment without achieving overall response will be counted as nonresponders.

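### The unpooled, unstratified Wald test for the primary response rate does not hold its stated 5% level: exact size is 6.2% (MDS) and 5.4% (AML) at the planned sizes if cytogenetic risk is not prognostic, and lower by an unknown amount if it is

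*SAP*

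**What the plan says.** - **Level.** The Protocol Summary (Statistical Methods) plans the MDS comparison "with a type I error rate of 5% and 90% power". AML has the same 5% rate with 80% power.
- **Test.** SAP 10.1 says the difference in response proportions will be "tested using a standard Wald asymptotic two-sided test with unpooled estimate of variance", and writes out a standard error with no stratum term. Protocol 9.6.1.1 agrees: "Test statistics on the difference of proportion of overall response between monotherapy arm and combination therapy arm using unpooled estimate of variance". SAP 10.2 applies the same method to the other response rates.
- **Randomization.** SAP 4.2 balances the arms dynamically within cytogenetic-risk group ("MDS: Very good, good and intermediate vs. Poor and Very Poor"; intermediate v poor for AML). When assigning to one arm would leave less imbalance, "Otherwise, the probability will be 9/1" in favour of that arm. Replaced subjects drop out of the balance count: "Only evaluable subjects will be considered when dynamic randomization is performed".
- **Population.** The ITT population "will include all randomized subjects. The primary efficacy analyses will be performed on the ITT Population". Replaced subjects therefore stay in the primary analysis although the balancing rule ignores them.
- **Stratified analysis elsewhere.** SAP 10.2 stratifies its log-rank tests by cytogenetic risk at randomization. The primary endpoint gets no such adjustment, and no reason is given.

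**The concern.** A Wald statistic with unpooled variance tends to reject too often at these sample sizes, because the estimated standard error is smallest when the observed proportions are far apart. Separately, if arms are balanced within a prognostic factor and the test ignores that factor, the standard error is too large for the design. The test then rejects too seldom and loses power. The plan combines both features, so the real level depends on how strongly cytogenetic risk predicts response and on the final arm split. Neither is known. The stated 5% is therefore nominal only, and a borderline comparison in either cohort can turn on the choice of variance.

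**Working it through.** **Inputs.** MDS: 36% v 72%, 72 subjects (36 per arm). AML: 25% v 50%, 110 subjects (55 per arm). Two-sided 5%, 1:1 (SAP 4.1, 4.3.1, 4.3.2). Test statistic from SAP 10.1. Response rates by risk group, sizes of the risk groups and replacement rates are not in the documents; every value used for them below is an assumption.

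**1. The plan's own sample size.** With unpooled variance, n per arm = (z₀.₉₇₅ + z_power)² × [p₁(1−p₁) + p₂(1−p₂)] / d².
- MDS: (1.960 + 1.282)² × (0.2304 + 0.2016) / 0.36² = 35.0, rounded up to 36 per arm, total 72.
- AML: (1.960 + 0.842)² × (0.1875 + 0.2500) / 0.25² = 54.9, rounded up to 55 per arm, total 110.

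Both totals are reproduced; power by this formula is 90.8% and 80.0%. The pooled-variance formula gives 88.2% and 78.1% at the same sizes, and would need 39 and 58 per arm (78 and 116) for 90% and 80%.

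**2. Exact size without strata.** Sum the product of the two binomial probabilities over all (x₁, x₂) with |z| > 1.96, both arms at the planned control rate.

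| Arms | Unpooled | Pooled |
|---|---|---|
| MDS 36/36 | 6.2% | 5.3% |
| MDS 35/37 | 5.5% | 5.0% |
| MDS 37/37 | 6.0% | 4.8% |
| MDS 38/38 | 5.5% | 4.9% |
| MDS 40/40 | 5.2% | 4.9% |
| MDS 42/42 | 5.6% | 5.4% |
| AML 55/55 | 5.4% | 5.0% |
| AML 54/56 | 5.5% | 5.0% |
| AML 58/58 | 5.7% | 5.2% |
| AML 60/60 | 5.3% | 5.2% |

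Across common rates of 26% to 46% (MDS, 36/36) the unpooled test runs 5.4% to 6.2% and the pooled test 4.6% to 5.4%. Across 15% to 35% (AML, 55/55) they run 5.4% to 5.7% and 5.0% to 5.3%. Exact power, unpooled v pooled, is 88.6% v 87.4% (MDS) and 80.2% v 78.9% (AML).

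**3. Effect of ignoring the stratum, exact.** Assume two equal risk groups, exactly balanced between arms. The planned test's size for a gap in response rate between groups of 0, 10, 20 and 30 points is:
- MDS: 6.2%, 6.1%, 5.7%, 5.0%
- AML: 5.4%, 5.3%, 4.8%, 4.0%

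It crosses 5% at a gap of about 30 points (MDS) and 17 points (AML).

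**4. Simulation of the SAP's 9:1 rule within stratum.** 100,000 null trials per row, Monte Carlo standard error about 0.07 points, equal risk groups assumed.

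| Assumed rates by risk group | Planned | Pooled, no strata | Stratified, unpooled | CMH |
|---|---|---|---|---|
| MDS, no difference | 6.0% | 5.1% | 6.3% | 4.8% |
| MDS 43%/29% | 5.6% | 4.8% | 6.2% | 4.8% |
| MDS 50%/22% | 4.8% | 4.1% | 6.0% | 4.8% |
| MDS 56%/16% | 3.8% | 3.3% | 6.2% | 4.9% |
| AML, no difference | 5.5% | 5.0% | 5.7% | 5.0% |
| AML 31%/19% | 5.3% | 4.8% | 5.7% | 5.0% |
| AML 38%/12% | 4.4% | 3.9% | 5.6% | 4.9% |
| AML 42%/8% | 3.7% | 3.4% | 5.9% | 5.0% |

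Only CMH stays near 5% in every row. Strata with unpooled variance stay above 5%, and pooled variance without strata drops below 5% once the factor is prognostic.

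**5. Replacement.** Assume 10% or 15% of subjects are replaced and stay in ITT as non-responders (mean ITT 80 and 85 for MDS, 122 and 129 for AML). The planned test has size 5.6% (no stratum difference) and 4.7% (50%/22%) in MDS, and 5.3% to 5.4% and 4.3% to 4.4% (38%/12%) in AML. CMH stays at 4.9% to 5.1%.

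**6. Power, planned v CMH** (40,000 trials per row, common odds ratio set to reach 72% and 50% overall).
- MDS: 88.9% v 87.5% (no difference), 88.8% v 88.0% (43%/29%), 89.5% v 90.4% (50%/22%).
- AML: 79.9% v 78.0% (no difference), 80.3% v 79.2% (31%/19%), 81.1% v 82.7% (38%/12%).

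**7. Borderline tables, unstratified.**
- MDS 18/36 v 10/36: d = 0.2222. Unpooled SE 0.1119, z = 1.986, p = 0.047. Pooled SE 0.1149, z = 1.934, p = 0.053.
- AML 28/55 v 18/55: d = 0.1818. Unpooled SE 0.0924, z = 1.967, p = 0.049. Pooled SE 0.0941, z = 1.933, p = 0.053.

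**The case against.** The plan does not contradict itself. Protocol and SAP agree on the test, the SAP writes it out, the same variance reproduces the sample sizes, and a Wald test agrees with its Wald interval. An asymptotic test is expected to miss its nominal level somewhat, and the pooled test also exceeds 5% at 36/36 and 42/42. The 6.2% is close to the maximum at 36 per arm (6.23%, at a common rate of 37%); a 35/37 split gives 5.5%. The stratum effect rests wholly on assumed rates, and stratifying the log-rank tests does not oblige anyone to stratify a binary test. This is an open-label Phase 2 study, and CMH loses power if the factor is not prognostic.

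Much of this stands. The net level may be at or below 5%, so the supportable claim is that 5% is not held, not that it is certainly exceeded. The effect is small. The borderline tables compare the planned test with a pooled unstratified one, so they show sensitivity to the variance, not what CMH would give. What does not stand is the appeal to consistency: a test that matches its sample-size formula need not have the stated level. Where the planned test falls well below 5%, it also gives up power to CMH.

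**Conclusion.** The concern holds, as an inexpensive improvement and not a major flaw. The unpooled variance alone puts the size at 6.2% (MDS) and 5.4% (AML) at the planned allocation and control rates. In the cases enumerated with no stratum effect, the excess over 5% is at most about 1.2 points for MDS and 0.7 points for AML. That part needs no assumption about strata. Ignoring the balanced cytogenetic-risk group pulls the level down, to 3.8% (MDS) and 3.7% (AML) under the strongest gaps assumed. Where the trial lies in that range cannot be known from the documents.

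**What to change.** In each cohort, make the primary test of overall response a Cochran-Mantel-Haenszel test stratified by cytogenetic-risk group as randomized. Change the variance and the strata together, since neither alone fixes the level. Report a stratified risk difference with a named score-type 95% interval, stating that test and interval may disagree narrowly at the boundary. Keep the unstratified Wald result as a sensitivity analysis, and let the change carry through to the secondary response rates in SAP 10.2.

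Restate planning power as about 87-88% (MDS) and 78-79% (AML) before any gain from stratification. The totals of 72 and 110 can then stay; holding 90% and 80% on the pooled formula would need 78 and 116.

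Two small edits belong with this. The MDS strata for the log-rank tests in SAP 10.2 should carry the full grouping used in SAP 4.2, including very good and good. The AML hematologic improvement rates should have score or exact intervals in place of Wald ones.

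The cost is SAP wording, standard software, and an entry in SAP Section 15 (or a protocol amendment) for the departure from Protocol 9.6.1.1. The downside is about 1 to 2 points of power if cytogenetic risk is not, or only weakly, prognostic for response (with no difference, MDS 88.9% to 87.5% and AML 79.9% to 78.0%).

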## Appendix K: Modified International Working Group AML Response Criteria (Cheson, 2003)

### Hematologic Response According to IWG Criteria for AML

Category	Definition
Morphologic Complete Remission (CR)	The following conditions should be met: 
 
ANC <math>\geq</math> 1,000/<math>\mu</math>Lb;
 
Platelet count <math>\geq</math> 100,000/<math>\mu</math>L;
 
The bone marrow should contain less than 5% blast cells;
 
Auer rods should not be detectable;
 
Independent of transfusions
 

Morphologic Complete Remission with Incomplete Blood Count Recovery (CRi)	Defined as a morphologic complete remission but the ANC count may be < 1,000/ $\mu$ L and/or the platelet count may be < 100,000/ $\mu$ L.
Cytogenetic Complete Remission (CRc)	Defined as morphologic complete remission with a reversion to a normal karyotype.
Partial Remission (PR)	Defined as an ANC $\geq$ 1,000/ $\mu$ L and platelet count $\geq$ 100,000/ $\mu$ L with a > 50% decrease in the percentage of bone marrow blasts to 5% to 25% (a blast count value of $\leq$ 5% may also be considered a partial remission if Auer rods are present). a, b
Relapse after CR or CRi	Defined as 1) the reappearance of > 5% blasts in the peripheral blood, or 2) a single finding of > 15% blasts in the bone marrow. All of the above occurrences should be attributed to relapse following CR or CRi and not attributable to another cause (eg, bone marrow regeneration after consolidation therapy) b .
Treatment Failure	Aplasia: Subject survives $\geq$ 7 days post chemotherapy; death while cytopenic, with aplastic bone marrow. Indeterminate Cause: 
 
Subjects who die < 7 days posttherapy
 
Subjects who die <math>\geq</math> 7 days posttherapy with no peripheral blood blasts, but no bone marrow examinationb
 
Subjects who die without completing the first course of therapy
 

Category	Definition

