The number and percentage of subjects who achieve each component of the overall response (CR, PR, mCR, HI-E, HI-P, HI-N) will be summarized together with associated two-sided 95% CI.

The best overall response per IWG 2006 response criteria will be summarized. The best overall response is defined as the best response prior to progressive disease and first subsequent therapy.

The below order will be considered for the definition of best response:

1. CR
2. PR
3. mCR
4. SD
5. PD
6. Disease transformation
7. Failure due to death
8. Not Evaluable/Missing

Acute Myeloid Leukemia Cohort

For the AML cohort, the primary efficacy endpoint is the proportion of subjects achieving an overall response rate (CR or CRi) based on modified IWG 2003 response criteria for AML ([Appendix 17.3](#)). The ORR will be summarized together with two-sided 95% CI. Subjects discontinued before 6-cycle treatment without achieving overall response will be counted as nonresponders.

The number and percentage of subjects who achieve CR, PR, CRi, HI-E, HI-P and HI-N will be summarized together with associated two-sided 95% CI

The best overall response per modified IWG response criteria will be summarized. The best overall response is defined as the best response prior to progressive disease and first subsequent therapy.

The below order will be considered for the definition of best response:

1. CR
2. CRi
3. CRc

4. PR
5. SD
6. PD
7. Treatment failure
8. Not Evaluable/Missing

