10.2. Secondary Efficacy Endpoints

Overall response rate and best overall response will also be provided according to the investigator assessment. Of note a response reported as Cytogenetic Complete Remission (CRc) in the eCRF would also be considered as CR in the summaries, CRc being a subset of CR.

Time to event data will be compared between treatment arms within each cohort using a log-rank test stratified according to their cytogenetic risk at time of randomization (intermediate vs poor and very poor for MDS and intermediate vs poor for AML).

Response rates will be compared between treatment groups using the same methodology for the primary endpoint.

Overall Survival

Overall survival is defined as the time between randomization and death/censored date. Subjects who die, regardless of the cause of death, will be considered to have had an event. Subjects who are alive at the time of clinical data cut-off date will be censored at the earlier between last assessment at which the subject was known to be alive and cut-off date will be used. All subjects who were lost to follow-up prior to the clinical data cut-off date will also be censored at the time of last contact. The stratified log rank test will be used to compare the time-to-event curves between Arm A and Arm B. The OS curve and OS at 6 and 12 months will be estimated and compared using Kaplan-Meier (KM) method.

Time-to-Response (TTR)

Time to onset of first response is defined as the time between the date of randomization and the earliest date any response (CR, PR, mCR, or HI for MDS Cohort, CR or CRi for AML Cohort whichever is the 1st) is observed. Subjects who do not achieve any defined response during the treatment period will be censored at the date of last adequate response assessment, disease progression, or death, whichever occurs first. Median time to onset of first response and associated two-sided 95% CI for the treatment group will be estimated using the KM method.

A sensitivity analysis of TTR will be performed for subjects who had responded. Summaries using descriptive statistics n, Mean, Standard Deviation (STD), Q1 and Q3, Median, Minimum (Min), and Maximum (Max) will be provided.

Duration of Response (DoR)

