17.3. Modified International Working Group AML Response Criteria (Cheson, 2003)

Hematologic Response According to IWG Criteria for AML

Category	Definition
Morphologic Complete Remission (CR)	
 • BM Blasts < 5% 
AND
 
 • All of the following peripheral blood values met: 
 ○ Platelets $\geq 100 \times 10^9/L$ ○ ANC $\geq 1.0 \times 10^9/L$ 
Where the date of the hematology assessment used is within the window -8 and +8 days of BM date. If multiple hematology assessments within this window, the closest to BM date should be used. If multiple on same distance to BM date, the one before BM date should be used
 
AND
 
 • No platelet, or whole blood transfusions for 1 week (7days) prior to the date of the hematology assessment used for the response evaluation
Morphologic Complete Remission with Incomplete Blood Count Recovery (CRi)	
 ▪ BM Blasts < 5% 
AND
 
 ▪ One or both of the following peripheral blood values met: 
 ▪ Platelets < $100 \times 10^9/L$ ▪ ANC < $1.0 \times 10^9/L$ 
Where the date of the hematology assessment used is within the window -8 and +8 days of BM date. If multiple hematology assessments within this window, the closest to BM date should be used. If multiple on same distance to BM date, the one before BM date should be used

Category	Definition
Cytogenetic Complete Remission (CRc)	
 ▪ CR criteria met 
AND
 
 ▪ Abnormal karyotype present at baseline 
AND
 
Reversion to normal karyotype at time of CR (based on ≥ 10 metaphases), where date of cytogenetic sample = date of BM sample used for the CR assessment

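### SAP 10.1 ranks cytogenetic complete remission (CRc) below CRi in the AML best-response order, although the SAP's own definitions make CRc a subset of CR

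*SAP*

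**What the plan says.** **The ranking.** SAP 10.1, under the AML cohort, summarises best overall response: "The best overall response is defined as the best response prior to progressive disease and first subsequent therapy". It continues "The below order will be considered for the definition of best response" and gives eight ranks: CR, CRi, CRc, PR, SD, PD, treatment failure, not evaluable/missing. The same two sentences also appear under the MDS cohort; this point concerns only the AML list.

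**The definition of CRc.** SAP 17.3 sets three conditions: "CR criteria met", an abnormal karyotype at baseline, and "Reversion to normal karyotype at time of CR". Protocol Appendix K agrees: "Defined as morphologic complete remission with a reversion to a normal karyotype".

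**The subset statement.** SAP 10.2 first says that response will also be summarised by investigator assessment. It then adds that a CRc reported in the eCRF "would also be considered as CR in the summaries, CRc being a subset of CR".

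**The primary endpoint.** For AML, "the primary efficacy endpoint is the proportion of subjects achieving an overall response rate (CR or CRi"), by the criteria in SAP 17.3. CRc is not named there. SAP 10.1 derives the primary response by program from central laboratory results.

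**The concern.** A category that requires full CR plus karyotype reversion is at least as deep as CR. Here it sits below CRi, the category for incomplete count recovery. A programmer who implements the list as printed, with one label per assessment, would report a subject who improves from CRi to CRc at the lesser level. A subject whose only response is CRc would appear under neither CR nor CRi.

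The one sentence that folds CRc into CR is written for responses reported in the eCRF and follows directly on the investigator assessment. No matching sentence covers the central derivation. What is at stake is the accuracy of the central AML best-response table and, under single labels, its agreement with the investigator table for the same subject.

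**Working it through.** The plan gives no figure to reproduce. The check applies the printed order to possible response paths.

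**Inputs.** The AML order comes from SAP 10.1 and the definitions of CR, CRi and CRc from SAP 17.3. Take five possible states at an assessment: CR without CRc, CRc criteria met, CRi, PR, SD. Take three assessments, for example the ends of Cycles 3, 6 and 9, with no progression and no subsequent therapy, so that all three count.

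**Two codings.** The SAP does not say outright which applies.
- Single label: an assessment that meets CRc is coded CRc only.
- Nested: an assessment that meets CRc is coded CR and CRc.

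**One subject, SD then CRi then CRc.**
- Single label: the codes are SD, CRi, CRc. The highest-ranked is CRi (rank 2), so best response is CRi.
- Nested: the codes are SD, CRi, CR and CRc. The highest-ranked is CR (rank 1), so best response is CR.

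**All paths that contain a CRc.** There are 5³ = 125 paths in total and 4³ = 64 without a CRc, so 125 − 64 = 61 contain at least one.

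Under single labels:
- Best response CR (path also has a CR without CRc): 125 − 2×64 + 27 = 24.
- Best response CRi (no such CR, but a CRi): 64 − 2×27 + 8 = 18.
- Best response CRc (neither): 27 − 8 = 19.
- Check: 24 + 18 + 19 = 61.

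Under nested labels, every one of the 61 paths holds a rank 1 code.

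| Coding | CR | CRi | CRc |
|---|---|---|---|
| Single label, SAP order | 24 | 18 | 19 |
| Nested, SAP order | 61 | 0 | 0 |

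These are counts of possible paths, not expected patient frequencies. They show that single labels misplace some subjects and that nested labels leave rank 3 unused. Under neither coding does the printed order work as a hierarchy.

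**Which coding the SAP favours.**
- SAP 17.3 defines CR by marrow blasts, platelets, neutrophils and freedom from transfusion. It has no karyotype exclusion, so every assessment that meets CRc also meets CR.
- The stable-disease definition in SAP 17.3 is a remainder category. Its list of the other categories is CR, CRi, PR, PD, treatment failure and not assessable. CRc is absent, which fits CRc lying inside CR.
- The second item is supporting evidence only. The corresponding stable-disease list for MDS in SAP 17.2 omits marrow CR, which is a separate category, so these lists are not reliably complete.
- Against nesting, SAP 10.1 gives CRc its own rank, which has a purpose only if CRc can be a label in its own right.

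On balance the definitions support nesting, but the ranking list does not fit it.

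**The case against.** The strongest case on the other side is that the definitions already settle the matter. A sample that meets CRc meets CR, CR is rank 1, and the program will find it. The reason given in SAP 10.2, that CRc is a subset of CR, is general. An explicit mapping is needed for eCRF data because an investigator may have reported CRc, whereas a criteria-based central derivation needs none. Complete cytogenetic response is also a separate AML secondary endpoint, summarised with a 95% CI among subjects with baseline cytogenetic abnormalities (SAP 10.2), so an empty CRc row loses nothing. On this view only a redundant line in a descriptive table remains.

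Most of this stands. Nesting is the better-supported reading, and under it nobody is mislabelled. Two things do not fall away. The printed order still contradicts the SAP's own definitions. And the only explicit instruction to count CRc as CR is tied to eCRF responses, which leaves the central program to choose between a definition and a list that disagree.

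**Conclusion.** The point holds as an inconsistency in a prespecified rule. Its reach is the descriptive central best-overall-response table for the AML cohort. Under single labels, CRi-to-CRc subjects are reported as CRi and CRc-only subjects as neither CR nor CRi. Under nested labels these subjects are correctly CR and the CRc rank is dead.

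A reader might infer three stronger things that the documents do not support.

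- **That CRc-only subjects drop out of the primary ORR.** SAP 10.1 defines ORR by achieving CR or CRi under the SAP 17.3 criteria. Nothing says it is read from best-response labels. A CRc subject has met CR by definition, so ORR is unaffected as long as CRc is counted as CR.
- **That the AML futility rule is distorted because it looks at the CR rate as a component.** This too would require CR to be counted from single labels that exclude CRc, contrary to SAP 17.3.
- **That the number of affected subjects can be estimated.** One might take 55 per arm (110/2), apply the 25% to 50% response rates and multiply by a guessed share with CRc. The documents give no such share. Responders include CRi-only subjects and subjects with a normal baseline karyotype, who are eligible as intermediate risk; neither group can be CRc. Even under single labels, a subject who also has an assessment labelled CR is still reported as CR.

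**What to change.** In SAP 10.1, replace the AML order with: CR (including CRc), CRi, PR, SD, PD, treatment failure, not evaluable/missing. Show CRc as an 'of which' row under CR. Add one sentence stating that the SAP 10.2 rule, by which CRc counts as CR, applies to the central derivation as well as to the investigator assessment.

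Moving CRc to the top of the list without that sentence would be incomplete: under single labels a CRc-only subject would still carry a label that is neither CR nor CRi.

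The cost is one edited list and one sentence. No new data are needed and no test changes. Every path in the check that contains a CRc is then reported as CR, with cytogenetic clearance still visible beneath it.
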